**Prospective, Comparative Assessment of Alveolar Bone Augmentation
Using GUIDOR® Membrane in the Bound Edentulous Space**

NCT number NCT02387008

Document Date November 11, 2015

CLINICAL STUDY PROTOCOL

Study Product: GUIDOR® Membrane

Study Code: 13-2429

Edition Number: Revision 04

Date: November 11, 2015

PROSPECTIVE, COMPARATIVE ASSESSMENT OF ALVEOLAR BONE AUGMENTATION USING GUIDOR® MEMBRANE IN THE BOUND EDENTULOUS SPACE

CLINICAL STUDY PROTOCOL

PROTOCOL SYNOPSIS

Sponsor
UNC School of Dentistry [name]

Coordinating and Principal Investigator

[name], University of North Carolina, USA

Study center(s) and number of subjects planned

The study will include a total of 60 subjects equally distributed at two centers:

Center 1: [name], University of North Carolina, USA

Center 2: [name], University of Southern California, USA

Study timetable

Estimated date of first subject Q4 2015
enrolled

Estimated date of last subject Q3 2016/Q4 2016
completed

Objectives

The primary objective of this study is to investigate volumetric osseous changes at 6 months following guided bone regeneration by calculating horizontal and vertical bone changes via cone beam computed tomography (CBCT).

Secondary objectives of the study are to evaluate soft tissue inflammation, soft tissue infection, and wound dehiscence..

Study design

The study is designed as a prospective, randomized controlled clinical trial. Patients will be assigned for guided bone regeneration of a single bound edentulous site to treatment group A (GUIDOR® membrane with freeze-dried bone allograft), group B (GUIDOR® membrane alone), or group C (Bio-Gide® membrane with freeze-dried bone allograft).

Target subject population

Patients in need of guided bone regeneration prior to dental implant therapy in a single, bound edentulous space within zone 14-24 or 34-44 will be included.

Investigational product

GUIDOR® membrane is a bioresorbable copolymer barrier membrane of polylactic acid blended with a citric acid ester. For this investigation 15 mm x 20 mm membranes will be utilized.

Comparator, dosage, and mode of administration

Bio-Gide® membrane is a porcine type I/type III non-cross-linked collagen bilayer membrane. The membranes are resorbed via collagenase over a 24 week period. The dense outer surface faces soft the overlying soft tissues, preventing epithelial or fibrous tissue ingrowth. The porous inner surface faces the bone and/or bone graft material and permits osteoblast ingrowth.

Mineralized freeze-dried cortical bone allograft (LifeNet Health) is a particulate bone graft material. It has a particle size of 250-1000 µm and is sterilized via Allowash XG® technology.

Duration of treatment

The study follow-up will be approximately 6-7 months. The treatment period includes guided bone regeneration in anticipation of future dental implant care. Follow-up visits following the guided bone regeneration will occur at 7 days, 14 days, 28 days, 6 months.

Outcome variables

Efficacy

Primary outcome variable:

- Horizontal and vertical bone changes at 6 months

Secondary outcome variables:

- Inflammation (refer to 4.2.2.1) or infection (refer to 4.2.2.2)
- Membrane exposure
- Soft tissue complications (refer to 4.2.2.3)

Patient reported outcomes

- Not applicable

Health economics

- Not applicable

Pharmacokinetics

- Not applicable

Safety

- Summarize all adverse events

Genetics

- Not applicable

Statistical methods

The primary outcome variables of dimensional horizontal and vertical bone changes will be analyzed by Wilcoxon rank sum test.

The secondary outcome variables assessing the presence or absence of inflammation, infection, and soft tissue complications (wound dehiscence, membrane exposure) will be analyzed by chi-square test.

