2 STUDY OBJECTIVES

2.1 Primary objective

The primary objective is to compare the horizontal and vertical changes in osseous dimension of a single bound edentulous zone following guided bone regeneration. Three different bone augmentation techniques will be used. Data will be obtained from DICOM images acquired by CBCT imaging. The dimensional location of the facial bone plate in the Z-axis and Y-axis will be reported in terms of a reference point (the mid-alveolar point positioned on a tangent drawn from the cementoenamel junctions of the mesial and distal adjacent teeth. The changes from baseline to six months will be compared.

Hypothesis: The treatment group with GUIDOR membrane with allograft is superior to comparative treatment groups (GUIDOR membrane alone or Bio-Gide® membrane with allograft).

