Pre-surgical antibiotic prophylaxis will be provided for patients at risk for infective endocarditis or with total joint replacement according to current guidelines provided by the American Dental Association, American Heart Association, and the American Academy of Orthopaedic Surgeons (9, 10).

Surgical Procedure

Sedation options will be discussed with the patient and a decision will be made to have:

- No sedation
- Oral conscious sedation

Anesthesia:

20% benzocaine topical anesthesia will be maintained for 1 minute. Infiltration anesthesia using 2% lidocaine with 1:100,000 and 2% lidocaine with 1:50,000 epinephrine will be provided. It is anticipated that 3.6 to 5.4cc will be used.

The product will be implanted according to the Instruction for Use. A crestal incision will be placed in the bound edentulous site with sulcular incisions extending to the distal line angles of the adjacent teeth. Vertical releasing incisions using a papilla sparing design will be extending to or beyond the mucogingival junction.

A full-thickness mucoperiosteal flap will be elevated and extended to permit access to the edentulous site requiring bone augmentation. Periosteal release with a new #15 blade and bone decortication of the edentulous site with a 1/4 round bur will be completed.

Bone graft material and barrier membranes will be placed within the confines of the adjacent osseous architecture accordingly:

- Group A: FDBA reconstituted in saline will be used to augment the edentulous site and will be covered by a GUIDOR® membrane.
- Group B: A GUIDOR® membrane will be placed over the edentulous site.
- Group C: FDBA reconstituted in saline will be used to augment the edentulous site and will be covered by a Bio-Gide® membrane.

Following completion of bone augmentation, the flaps will be reapproximated and primary closure will be achieved using 5-0 (CV-6) ePTFE suture in the areas of the crestal and sulcular incisions and 5-0 chromic gut suture in the areas of the vertical releases. It is anticipated that horizontal mattress, vertical mattress, continuous interlocking, and/or simple loop sutures will be employed.

Post-Surgical Procedures

Post-surgery, infiltration anesthesia with 0.5% bupivacaine with 1:200,000 will be provided. It is anticipated that 1.8cc will be used.

Post-surgical antibiotic coverage will be provided to patients. It is recommended that a 7-day course of 500mg Amoxicillin every 8 hours or 300mg Clindamycin every 6 hours will be provided.

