4. Edentulous for at least 6 months at study site
5. A buccal-lingual ridge width at study site of ≤ 4 mm

6. A mesial-distal distance between adjacent teeth at study site at bone level of at least 5 mm
7. A keratinized mid-buccal mucosal thickness of at least 2 mm at study site (measured buccally at MD midline from the mucogingival junction to the projected alveolar ridge crest)
8. Teeth adjacent (mesial and distal) to study site must consist of two stable, natural teeth without signs of periodontal bone loss (> 3 mm) and/or significant soft tissue loss
9. A minimum of twenty teeth in good repair

Exclusion criteria

Any of the following is regarded as a criterion for exclusion from the study:

1. Insufficient interocclusal distance for future dental implant placement and restoration
2. More than 3 mm vertical bone loss at study site as measured from the mid-buccal crest of bone on the adjacent teeth
3. Previous site development (soft and/or bone tissue) performed at the study site
4. Untreated rampant caries and uncontrolled periodontal disease
5. A history within the last 6 months of the daily use of any tobacco products besides cigarettes (smokeless chewing tobacco, e-cigarette, pipe or cigar smoking), or of smoking more than 10 cigarettes per day.
6. Current alcohol dependency, alcohol abuse or chemical dependency based on DSM-IV Criteria or drug abuse
7. Subjects having uncontrolled endocrine-induced diseases (e.g. uncontrolled diabetes mellitus and hyperparathyroidism)
8. Systemic or local disease or condition that would compromise post-operative healing and/or osseointegration
9. Use of any substance or medication that will influence bone metabolism (e.g. intravenous bisphosphonates)
10. Need for systemic corticosteroids or any other medication that would influence post-operative healing and/or osseointegration
11. History of radiation in the head and neck region > 30 Gy
12. Subject reports pregnancy or is nursing at the time of enrollment

13. Unable or unwilling to return for follow-up visits for a period of 6 months
14. Unlikely to be able to comply with study procedures according to Investigators judgement
15. Previous enrollment or randomization of treatment in the present study
16. Participation in another clinical trial within 30 days of enrollment

Restrictions

Subjects will be advised of the following restrictions during the study period:

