6.2 Method of statistical analysis

Primary objective

The primary objective is to compare dimensional bone changes from baseline (Visit 2) to six months (Visit 7) occurring in a single bound edentulous space following alveolar bone regeneration using three different techniques.

Assume the change (in the mid-buccal horizontal bone dimensions from baseline to six months) is denoted C_A , C_B and C_C , for group A, B and C, respectively. The null-hypotheses (two) is then to test if:

$$H_0: C_A = C_i \quad (i = B \text{ and } C, \text{ respectively})$$

can be rejected and hence

$$H_1: C_A \neq C_i \quad (i = B \text{ and } C, \text{ respectively})$$

accepted.

H_0 will be tested by means of the Wilcoxon rank sum test. A p-value less than 5% will be regarded statistically significant.

Secondary objectives

Secondary objectives of the study are to evaluate and compare clinical healing parameters between different grafting techniques (i.e. to compare between groups A, B, and C):

- Inflammation by assessing the presence or absence of soft tissue erythema within 3 mm from the crestal incision at 1 week, 2 weeks, 4 weeks, and 6 months following bone augmentation. The chi-squared analysis will be used.
- Infection by determining the presence or absence of suppuration or soft tissue fluctuance at 1 week, 2 weeks, 4 weeks, and 6 months following bone augmentation. The chi-squared analysis will be used.
- Soft tissue complications by determining the presence or absence of membrane exposure or soft tissue dehiscence at 1 week, 2 weeks, 4 weeks, and 6 months following bone augmentation. The chi-squared analysis will be used.

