6.3 Determination of sample size

A sample size of 20 participants per treatment group was selected following power calculations and allowing for 10% patient dropout. A sample size of 18 patients was calculated for the primary outcome variable (horizontal bone changes) with the assumption that the detectable difference would amount to 0.5 mm with a standard deviation of 0.5. The type I error probability was set at 0.05 and the statistical power was set at 80%.

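### The synopsis and sections 2.1 and 4.2.1.1 make horizontal and vertical bone change primary, but sections 6.2 and 6.3 define and size the trial for horizontal change only; vertical change has no hypothesis in section 6, no power basis and no error control

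*Combined protocol and SAP*

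**What the plan says.** Four places treat both dimensions as primary:

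- The synopsis, under outcome variables, lists as primary "Horizontal and vertical bone changes at 6 months".
- The synopsis, under statistical methods, gives both the same test: "The primary outcome variables of dimensional horizontal and vertical bone changes will be analyzed by Wilcoxon rank sum test".
- Section 2.1 states: "The primary objective is to compare the horizontal and vertical changes in osseous dimension of a single bound edentulous zone following guided bone regeneration". Its hypothesis is that GUIDOR with allograft (group A) is superior to both comparators, and it does not say on which dimension.
- Section 4.2.1.1, under the primary outcome heading, derives change in width (Z-axis) and in height (Y-axis).

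Two places treat only horizontal change as primary:

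- Section 6.2 opens with dimensional bone changes in general, then defines the quantities to be tested: "Assume the change (in the mid-buccal horizontal bone dimensions from baseline to six months) is denoted" by group. It gives two null hypotheses, A against B and A against C, each tested by Wilcoxon rank sum at 5%.
- Section 6.3 gives 18 per group as "calculated for the primary outcome variable (horizontal bone changes"), from a 0.5 mm difference, SD 0.5 mm, type I error 0.05 and 80% power.

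Vertical change is not among the secondary objectives in 2.2 or 6.2. Section 6.1 says that conclusions rest on the primary objective and that multiplicity is thereby accounted for. It also says that a separate analysis plan may be prepared, so none is guaranteed.

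**The concern.** The primary outcome decides what the trial may claim, and here that depends on which section is read. Suppose horizontal change shows no difference and vertical change gives p = 0.03 for one contrast. A reader of the synopsis and 2.1 could report superiority on a primary outcome. A reader of 6.2 would say that no primary hypothesis was rejected. Nothing in the plan settles this before the data are seen.

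The same gap affects error control. Section 6.1 relies wholly on conclusions being confined to the primary objective. That gives little protection if the objective holds two outcomes and two contrasts, each tested at 5% with no rule for combining them. A vertical result that is not significant would also be hard to read, because the plan does not say what vertical difference it was meant to detect.

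**Working it through.** **Step 1. Is there a planning basis for vertical change?**

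| Element | Horizontal | Vertical |
|---|---|---|
| Named primary (synopsis, 2.1, 4.2.1.1) | yes | yes |
| Test named in synopsis | Wilcoxon | Wilcoxon |
| Null hypotheses in 6.2 | two | none |
| Planning difference and SD in 6.3 | 0.5 mm, 0.5 mm | none |
| Multiplicity rule | none beyond 6.1 | none beyond 6.1 |

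**Step 2. Reproduce the plan's sample size (horizontal).** The inputs from 6.3 are a difference of 0.5 mm, SD 0.5 mm and 80% power, with alpha 0.05 two-sided (6.1).

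- Normal approximation: n = 2(1.960 + 0.842)² × (0.5/0.5)² = 15.7, so 16 per group.
- Two-sample t test: 16.7. Dividing by the Wilcoxon efficiency of 0.955 gives 17.5, so 18 per group, as stated.
- Simulated Wilcoxon power at 18 per group: 80.7%.
- Dropout: 18/0.9 = 20 per group, as stated.

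The horizontal calculation is sound on its own inputs.

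**Step 3. What does 18 per group give for vertical change?** The documents state no vertical difference or SD, so every value below is an assumption. The table shows simulated Wilcoxon power, two-sided 0.05, 18 per group.

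| True vertical difference | SD 0.5 mm | SD 0.75 mm | SD 1.0 mm |
|---|---|---|---|
| 0.25 mm | 28% | 15% | 11% |
| 0.5 mm | 81% | 46% | 28% |
| 0.75 mm | 99% | 81% | 56% |
| 1.0 mm | over 99% | 97% | 80% |

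The smallest difference with 80% power is about 0.98 SD: 0.49, 0.74 or 0.98 mm at the three SDs. Power runs from 11% to over 99%, and the documents cannot say where in that range the trial falls.

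**Step 4. How many primary tests are there, and what is the error rate?**

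- Under 6.2: one dimension × two contrasts = 2 tests.
- Under the synopsis and 2.1, with the two contrasts of 6.2: two dimensions × two contrasts = 4 tests.
- If all tests were independent: 1 − 0.95² = 9.75% for two tests and 1 − 0.95⁴ = 18.5% for four.
- The tests are not independent, because both contrasts use group A. Simulating Wilcoxon tests with A shared and no true difference (normal data, 18 per group) gives about 8.6% for the two horizontal tests. With the two dimensions independent, four tests give 1 − (1 − 0.086)² = about 16.5%.
- Width and height change come from the same site and may be correlated. With 18 to 20 per group, and correlations from 0 up to about 0.7, the four-test figure is about 14-17%. As the correlation approaches 1 it falls back towards the two-test figure.

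**The case against.** The strongest reply is that this is a drafting slip with little consequence. The synopsis does name a test for vertical change, and 6.2 merely fails to repeat it. Vertical change is measured by a masked analyst at Visits 2 and 7. If its difference and SD matched the horizontal planning values, power would be about 81%. All of this stands. It means that vertical change can be estimated and tested, but not that the plan says whether such a test is primary, what difference it is meant to detect, or how error is controlled across four tests.

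A second reply is that the two-contrast error rate of about 9% exists without vertical change. That is correct and is a separate matter. The point here is the further rise to about 14-17%.

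A third reply is that moving vertical change to secondary is not the only way to reconcile the text. That is also right. Keeping both dimensions primary would work if section 6 gained the missing pieces.

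A reader might go further and infer that vertical change has almost no room to occur, so that this half of the objective cannot be answered. The basis would be the exclusion of sites with "More than 3 mm vertical bone loss at study site as measured from the mid-buccal crest of bone on the adjacent teeth", the absence of a minimum vertical deficit, and the instruction that graft and membrane "will be placed within the confines of the adjacent osseous architecture". The documents do not support this. They give no distribution of baseline vertical deficit. The placement wording is not tied to a vertical limit. Any such ceiling would restrict gain and not loss, and loss also counts as change. The 1.24 mm height reduction cited in section 1.2 describes undisturbed sockets over 6 months, while study sites must have been edentulous for at least 6 months, so it is not a measure of room for gain here.

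**Conclusion.** The point holds as an inconsistency about which outcome is primary. It has two consequences. Vertical change has no hypothesis in section 6 and no power justification, with power anywhere from 11% to over 99% over the assumed values. If it counts as primary, the chance of at least one false primary claim rises from about 9% to about 14-17%, so the assurance in section 6.1 fails. The error rates assume no true difference between groups, normally distributed changes, 18 to 20 per group, group A shared, and a correlation between dimensions of 0 to about 0.7. The 9.8% and 18.5% figures apply only if all tests were independent.

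The point does not show that vertical change is untestable or limited by design, and the horizontal sample size is not in question. It should be corrected because it changes what the trial may claim.

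**What to change.** Name mid-buccal horizontal change from Visit 2 to Visit 7 as the single primary outcome in the synopsis (objective, outcome variables and statistical methods), 2.1 and 4.2.1.1. Narrow the opening sentence of 6.2 to match. Sections 6.2 and 6.3 already work this way for the hypotheses and sample size.

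List vertical change as a secondary outcome in 2.2 and 6.2, keeping the Y-axis measurement and the Wilcoxon test. Report it with the baseline vertical dimension from the Visit 2 CBCT, and state that it cannot by itself support the superiority claim in 2.1.

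This costs protocol wording only: no new data, visits or subjects. The small loss is a vertical primary claim for which the trial states no power. If the sponsor wishes to keep vertical change primary, section 6 needs vertical hypotheses, a sourced difference and SD, a rule for what counts as success across the two dimensions, and a multiplicity adjustment. That could alter the sample size.

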1 INTRODUCTION

1.1 Background

Guided bone regeneration refers to the use of occlusive membranes to permit access of selective cell populations to an osseous defect (1). It is based on the principle that fibroblast migration occurs at a rate faster than cells with osteogenic potential. As such placement of occlusive membranes creates a secluded space to allow for bone regeneration without disruption by fibroblast infiltration (1, 2). The principles of guided bone regeneration have been used for localized alveolar ridge augmentation to increase bone dimensions prior to dental implant treatment.

Functional requirements of barrier membranes include biocompatibility, cell occlusiveness, space maintenance, integration with the host tissues, and good clinical handling (3). Two types of barrier membranes are commonly used in alveolar ridge augmentation: non-resorbable and resorbable barrier membranes. Non-resorbable membranes necessitate a second surgical procedure for membrane removal and are associated with increased complications and infection in cases of membrane exposure during the healing period. Resorbable barrier membranes offer the advantages of increased biocompatibility and integration. However, their resorption rate must be controlled so that they are able to maintain space for a prerequisite period of time to permit bone regeneration. Resorbable barrier membranes must also be associated with minimal inflammatory reactions that do not negatively affect the degree of bone regeneration achieved (3-5).

Bone replacement grafts are commonly used in conjunction with barrier membranes to aid in space maintenance while providing a scaffold for bone regeneration. A variety of bone graft options are available, including autogenic, allogenic, xenogenic, and alloplastic options. Mineralized allografts have the benefit of providing an osteoconductive scaffold with a potential for osteoinductive properties following demineralization of the graft particles by osteoclasts (6). Their use is commonplace in clinical practice due to their osteoconductive, scaffolding properties.

Following guided bone regeneration, mean horizontal ridge width gains of 4.2 mm may be anticipated with use of a resorbable barrier membrane (7). Implant survival rates of 97-100% have been reported using a staged guided bone regeneration technique (7, 8).

1.2 Rationale

This study is intended to provide statistically robust evidence that guided bone regeneration outcomes using a GUIDOR® membrane with allograft is similar or better to outcomes obtained using other commercially available barrier membranes with allograft. It is intended to define in objective and subjective terms the response of the bone and overlying soft tissues to localized ridge augmentation. To fulfill the goals of this project,

the clinical study will seek to enroll patients with a single bound edentulous space that requires ridge augmentation prior to dental implant treatment.

It has been shown that the undisturbed, healed socket will lead to a loss of alveolar bone with a mean width reduction of 3.8 mm and height reduction of 1.24 mm within 6 months (9). Schropp et. al (2003), found, according to subtraction radiography, that by 12 months, the alveolar bone present after tooth extraction decreased by up to 50% of its original width (10). Buser, et. al (1990), reported a mean gain of 1.5-5.5mm of new bone formation 6-10 months post-GBR (11). Based on these studies, a significant difference should be observed, especially between the bone grafting group and the control group.

The goal of guided bone augmentation is to provide an alveolar ridge of sufficient dimension to permit dental implant placement. The healing of these sites should occur with an absence of inflammation and other complications.

This prospective clinical evaluation will enroll sufficient participants to perform statistical analyses of primary objectives. Additional information regarding the presence or absence of inflammation, infection, or other wound healing complications will also be obtained through the projected enrollment.

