6 STATISTICAL METHODS AND DETERMINATION OF SAMPLE SIZE

6.1 Statistical evaluation – general aspects

A comprehensive Statistical Analysis Plan (SAP) may be prepared before database lock. When using the terminology descriptive statistics it means that number of patients, mean, median, standard deviation, minimum and maximum values will be presented for continuous data and frequencies and percentages for categorical data.

If nothing else is stated, descriptive statistics will be given for each variable in the study and p-values may be complemented by confidence intervals as appropriate. All p-values presented will be two-sided. A p-value less than 5% will be called “statistically significant” but all conclusions will be based on the primary objective and hence multiplicity is accounted for even though careful interpretations are necessary as multiple tests are performed.

Analysis populations are defined as follows:

- The Intent-to-Treat (ITT) population includes all enrolled subjects who underwent guided bone regeneration procedure.
- The Per-Protocol (PP) population includes all enrolled subjects who had successful guided bone regeneration procedure and no major protocol deviations (defined as inclusion/exclusion or informed consent violations.)

The ITT population will be the primary analysis population for all endpoints. Analyses on the PP population will be supportive of the ITT analyses.

Demographics and other baseline characteristics

Demographics and other baseline characteristics will be presented by means of descriptive statistics (by group and in total). Continuous variables will be presented by means of number of observations (N), minimum (min), median, maximum (max), mean, and standard deviation (std). Discrete variables will be presented by frequency and percentage.

Covariates and prognostic variables

No covariates are judged to influence the outcome of the primary or any of the secondary variables.

Handling of dropouts and missing data

Patients dropping out from the trial prior to study end will not be replaced. Data totally missing will not be estimated.

Multicenter

This study is a multicenter study. However, there is not a priori reason to suspect that there will be any qualitative differences between the centers regarding any of the efficacy variables nor regarding the safety variables. Therefore, the primary statistical analyses will not include center in the model.

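### Section 1.2 aims to show that GUIDOR plus allograft is similar or better, but the design can show only a difference, and no interval for A minus C is required

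*Combined protocol and SAP*

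**What the plan says.** The relevant statements, all in the combined protocol:

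- **1.2 Rationale.** The study is meant to yield robust evidence that "outcomes using a GUIDOR® membrane with allograft is similar or better to outcomes obtained using other commercially available barrier membranes" with allograft. The same section later says that "a significant difference should be observed, especially between the bone grafting group and the control group".
- **2.1 Primary objective.** The objective is worded as a comparison of bone changes. The hypothesis attached to it is: "The treatment group with GUIDOR membrane with allograft is superior to comparative treatment groups".
- **6.1 General aspects.** P-values are two-sided, and "all conclusions will be based on the primary objective". Intervals are permitted but not required: "p-values may be complemented by confidence intervals as appropriate". Descriptive statistics (number, mean, median, SD, minimum, maximum) are promised for each variable. On a separate plan: "A comprehensive Statistical Analysis Plan (SAP) may be prepared before database lock".
- **6.2 Method of statistical analysis.** There are two null hypotheses of equality in mid-buccal horizontal change, A versus B and A versus C, with two-sided alternatives. "H_0 will be tested by means of the Wilcoxon rank sum test", at 5%.
- **6.3 Sample size.** 18 evaluable per group, 20 with dropout, assuming that "the detectable difference would amount to 0.5 mm with a standard deviation of 0.5", with type I error 0.05 and 80% power.

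The document contains no non-inferiority or equivalence margin, no such hypothesis, no interval-based decision rule, and no statement of how a non-significant A versus C result will be read.

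**The concern.** The stated purpose has two halves. *Better* is served by 2.1, 6.2 and 6.3, which fit together. *Similar* is served by nothing. A test of equality that fails to reject does not show that two treatments are alike. That needs an interval set against a margin fixed in advance.

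The gap matters most for A versus C. Both groups receive allograft and differ only in the membrane, so a non-significant result is quite possible there. If it occurs, 1.2 gives an author grounds to report that the membranes performed similarly, while 2.1 and 6.1 support only the statement that superiority was not shown. The plan does not require the report to display the interval that would tell these two apart.

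**Working it through.** **Inputs.** From 6.3: 18 evaluable per group, SD 0.5 mm, difference 0.5 mm, alpha 0.05, power 80%, dropout 10%. From 6.1 and 6.2: two-sided Wilcoxon test. The deficits and margins below are assumptions, because the document gives none.

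**1. The plan's sample size.**
- Normal approximation: 2 × (1.960 + 0.842)² × 0.5² / 0.5² = 15.7, so 16 per group.
- Based on the t distribution: 16.7, so 17.
- Divided by the Wilcoxon test's efficiency under normality: 16.7 / 0.955 = 17.5, so 18.
- With dropout: 18 / 0.90 = 20.

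The stated 18 and 20 reproduce as a two-sided superiority calculation.

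**2. Precision of A minus C.**
- Standard error: 0.5 × √(2/18) = 0.1667 mm.
- 95% half-width: t(0.975; 34) × 0.1667 = 2.032 × 0.1667 = 0.339 mm.
- Simulated mean half-width of the Hodges-Lehmann interval (100,000 normal trials): 0.350 mm, coverage 95.3%.

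**3. How often a real deficit of A would be non-significant.** With noncentrality = deficit / 0.1667 and 34 degrees of freedom, a 0.3 mm deficit gives 0.3 / 0.1667 = 1.8 and a probability of 0.583 that p exceeds 0.05. Wilcoxon figures are simulated.

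| Assumed true deficit of A | Non-significant, t | Non-significant, Wilcoxon |
|---|---|---|
| 0.2 mm | 79% | 80% |
| 0.25 mm | 69% | 72% |
| 0.3 mm | 58% | 61% |
| 0.5 mm | 17% | 20% |

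**4. What 18 per group would give if similarity were a formal aim.** Non-inferiority power, one-sided 2.5%, true difference zero, noncentrality = margin / 0.1667:

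| Assumed margin | Power (t) |
|---|---|
| 0.5 mm | 83% (Hodges-Lehmann, simulated: 80%) |
| 0.4 mm | 64% |
| 0.3 mm | 42% |
| 0.2 mm | 21% |

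Whether the trial could support similarity therefore depends on a margin that the plan does not state.

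**The case against.** The best defence is that the operative sections already settle the matter. Section 1.2 is background; the hypothesis, test and sizing all point to superiority, and 6.1 ties conclusions to the primary objective. No sentence says that non-significance will be read as similarity. Most of this stands. The limit in 6.1 is indirect, however, because 2.1 words the objective itself as a comparison, and the caution on interpretation in 6.1 concerns multiple testing. Section 1.2 also states what the study is intended to deliver, so it is more than a literature summary.

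Reporting is also less bare than it may seem. Section 6.1 promises number, mean and SD, and 4.2.1.1.2 promises averages by treatment group, so a reader could derive a t interval. What is missing is a required, displayed interval that matches the Wilcoxon test.

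A reader might draw four stronger conclusions that the documents do not support:

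- *The test or the sample size is wrong.* Both fit the hypothesis in 2.1. At an assumed margin of 0.5 mm, 18 per group would even give about 80% to 83% non-inferiority power.
- *The design can show only that A is better.* The test is two-sided and could also show A to be worse.
- *Section 1.2 contradicts itself by predicting an A versus C difference.* Its expectation of a significant difference mainly concerns graft against control.
- *A non-significant result would carry no information.* If A and C were truly equal, 82% to 85% of non-significant trials would exclude a 0.5 mm deficit. That line is only a benchmark, since 0.5 mm is the detectable difference and not a justified margin. If A were truly 0.3 mm worse, 64% to 68% of non-significant trials would fail to exclude it.

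**Conclusion.** The point holds as a mismatch between the stated aim and the design. Section 1.2 promises evidence of similarity that 2.1, 6.2 and 6.3 cannot provide, and no interval for A minus C has to be shown. The primary test remains valid for the superiority hypothesis, so this should be corrected but does not threaten the main analysis.

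On the plan's own n and SD, the interval extends about 0.34 to 0.35 mm either side of the estimate, and a 0.3 mm deficit would be missed in 58% to 61% of trials. These figures assume normally distributed changes, an SD of 0.5 mm and 18 evaluable per group. The 0.3 mm deficit is hypothetical: nothing in the document suggests that A is worse than C, or says what deficit would matter.

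**What to change.** 1. In 6.2, require the two-sided 95% Hodges-Lehmann interval for A minus C in mid-buccal horizontal change, which matches the planned Wilcoxon test. Require the same for vertical change if it is tested; the synopsis lists it for the Wilcoxon test, but the hypotheses in 6.2 cover only horizontal change.
2. In 6.2, state that a non-significant A versus C result on these measures means that superiority was not shown and is not evidence of similarity. This need not extend to the soft tissue outcomes, for which 6.2 names no A versus C pair.
3. In 1.2, delete *similar or*, so that it agrees with 2.1.

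The cost is one interval, one sentence and two deleted words, with no extra patients and no change of test. These changes belong in the protocol, because the separate SAP is optional. The downside is that the sponsor gives up a similarity claim.

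If the sponsor prefers to keep that aim, it should instead fix and justify a non-inferiority margin before any by-group look at the data, and state the power that 18 evaluable per group gives at that margin. The 0.5 mm in 6.3 is not a justified margin merely because the trial was sized on it. Any supporting per-protocol analysis should not select patients on a successful procedure as 6.1 now does: success is undefined and could depend on outcome.
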